8.3.6.2. Secondary Endpoint Analysis

Endpoints that supplement the primary objective by further characterization of the effects of albiglutide on cardiovascular outcomes endpoints:

- MACE superiority will be evaluated using the same Cox regression model as the primary analysis of MACE non-inferiority.
- Supportive endpoints including the time to first occurrence of adjudicated MACE or urgent revascularisation for unstable angina, time to first occurrence of individual components of MACE, time to first occurrence of cardiovascular death or hospitalisation for heart failure will be analyzed using a proportional Cox regression model similarly as the primary endpoint.

Endpoints that evaluate the effects of albiglutide on metabolic management of type 2 diabetes:

- Among the subjects who are not on insulin at baseline (NI population), time to insulin will be analyzed using a proportional Cox regression model similar to the primary MACE analysis. The product-limit estimates of the probabilities (and their standard errors) of adding insulin over time will be computed and displayed as Kaplan-Meier (KM) survival curves for albiglutide and placebo treatment groups. The KM curves will also be presented corresponding to the above comparisons.
- Composite of the proportion of those achieving good control ($HbA1c \leq 7.0\%$) AND no severe hypoglycaemic incidents AND weight gain $<5\%$ at the end of the study would be evaluated utilize nonparametric, covariance-adjusted, extended Mantel-Haenszel tests. Additional analysis will be provided for scheduled visits. Nominal p-values and 95% CIs will be presented for these visits. Time to introduction of prandial insulin in those on basal insulin \pm orals anti-hyperglycemic drugs at baseline will be analyzed using PH model / log-rank test and KM method similar to the primary endpoint.
- Composite of microvascular events will be analyzed using a proportional Cox regression model / log-rank test and KM method similar to the primary endpoint.

- HbA1c, body weight and eGFR will be analyzed using a repeated mixed effect model. The least square means, 95% CIs and nominal p-values will be presented.
- Additional analysis will be performed to assess the incidence rate of recurrent severe hypoglycaemic events between treatment groups during the course of the study. A repeated Poisson regression model including treatment and visit as factors will be used to test treatment difference with offset for person years. An unstructured working correlation matrix will be used in the iterative estimation process. The model-adjusted least square incidence rate for each treatment as well as the treatment difference of the incidence rate will be reported. Events of severe hypoglycaemia will also be summarized descriptively by treatment group. Additional summary by baseline HbA1c, renal status and age subgroup will also be provided.

Further analysis details will be provided in the RAP.

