In order to evaluate satisfaction with treatment and to compare satisfaction across treatment groups, the TRIM-D questionnaire will be self administered by all subjects at baseline and at each 8 month visit (and, to the extent possible, at the time of study completion or withdrawal from the study).

Amended Text:

In order to evaluate satisfaction with treatment and to compare satisfaction across treatment groups, the TRIM-D questionnaire will be self administered by all subjects at baseline (except for subjects whose diabetes is treated by diet and exercise alone) and all subjects at each 8 month visit (and, to the extent possible, at the time of study completion or withdrawal from the study).

Section 8.3.3.1 Primary Comparisons of Interest, second sentence*Original text:*

The primary endpoint will be the time to the first occurrence of MACE over the full duration of the study. A p-value for the primary endpoint will be calculated from a Cox regression model with treatment group as the only covariate for the hypotheses described in Section 8.1.

Amended text:

The primary endpoint will be the time to the first occurrence of MACE over the full duration of the study. A p-value for the primary endpoint will be calculated from a Cox **Proportional Hazards (PH)** regression model with treatment group as the only covariate for the hypotheses described in Section 8.1.

Section 8.3.3.2. Other Comparisons of Interest, insertion of two new sentences:*Original text:*

For other analyses incidence rates will be presented for binary data and summary statistics (mean, median, standard deviation, minimum, and maximum) will be presented for continuous data. Furthermore, summary statistics of change from baseline for HbA1c will be presented along with percent of subjects within ranges of clinical interest (e.g., HbA1c < 7.0%).

Amended text:

For other analyses incidence rates will be presented for binary data and summary statistics (mean, median, standard deviation, minimum, and maximum) will be presented for continuous data. **Time to event endpoints will be evaluated via the p-value from a Cox PH regression model with treatment as the only covariate.** Furthermore, summary statistics of change from baseline for HbA1c will be presented along with percent of subjects within ranges of clinical interest (e.g., HbA1c < 7.0%). **Available lipid data will be summarized for descriptive purposes.**

Section 8.3.6.2. Secondary Endpoint Analysis*Original text:*

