4. SUBJECT SELECTION AND WITHDRAWAL CRITERIA

4.1. Inclusion Criteria

Specific information regarding warnings, precautions, contraindications, AEs, and other pertinent information on the GSK investigational product or other study treatment that may impact subject eligibility is provided in the IB for albiglutide and in the product label for those countries where marketing authorisation has been granted.

Deviations from inclusion criteria are not allowed because they can potentially jeopardise the scientific integrity of the study, regulatory acceptability or subject safety. Therefore, adherence to the criteria as specified in the protocol is essential.

A subject will be eligible for inclusion in this study only if all of the following criteria apply:

1. Men or women at least 40 years old with a diagnosis of type 2 diabetes.
2. Established cardiovascular disease, including at least 1 of the following:
 - a. Coronary artery disease with EITHER of the following:
 - Documented history of spontaneous myocardial infarction, at least 30 days prior to Screening.
 - Documented coronary artery disease (CAD) \geq 50% stenosis in 1 or more major epicardial coronary arteries, determined by invasive angiography, or history of surgical or percutaneous (balloon and/or stent) coronary revascularization procedure (at least 30 days prior to Screening for percutaneous procedures and at least 5 years prior to Screening for coronary artery bypass graft (CABG)).
 - b. Cerebrovascular disease – ANY of the following:
 - Documented history of ischaemic stroke, at least 90 days prior to study entry.
 - Carotid arterial disease with \geq 50% stenosis documented by carotid ultrasound, magnetic resonance imaging or angiography, with or without symptoms of neurologic deficit.
 - Carotid vascular procedure (e.g. stenting or surgical revascularisation), at least 30 days prior to Screening.
 - c. Peripheral arterial disease (PAD) with EITHER of the following:
 - intermittent claudication and ankle:brachial index $<$ 0.9 in at least one ankle

- prior non-traumatic amputation, or peripheral vascular procedure (e.g. stenting or surgical revascularisation), due to peripheral arterial ischaemia.
3. HbA1c >7.0% (53 mmol/mol) based on the most recent documented laboratory assessment measured no more than 6 months prior to randomization. Local laboratory HbA1c values taken as part of usual care are permitted.

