8.3. Data Analysis Considerations**8.3.1. Analysis Populations**

The intent-to-treat (ITT) population will include all randomly assigned subjects. The ITT subjects will be analyzed according to randomised treatment. The inference for primary objectives in the study will be made from ITT population.

Per-protocol Population (PP) will exclude the subjects who have major protocol violations. Per-protocol analysis will include Per-protocol population only and their data upon to the time of discontinuation of investigational product plus 56 days.

The non-insulin population (NI) will include all subjects in the ITT population who are not on insulin at baseline. Inference for the time to insulin endpoint will be made from the NI population.

The baseline basal insulin user population (BI) will include all subjects in the ITT population who are on basal insulin, but not on other insulin at baseline. Inference for the time to prandial insulin endpoint will be made on BI population.

The safety population will include all enrolled subjects who receive at least 1 dose of study treatment. The safety population subjects will be analyzed according to the treatment received. The safety population will be used for analyses of safety objectives.

Other analysis populations will be defined in the RAP.

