8.3.5. Multiplicity Controls

A multiple comparisons adjustment strategy will be implemented for the multiple inferential tests among the primary endpoint and secondary endpoints of MACE superiority, time to insulin and composite metabolic endpoint.

The strategy will use a combination of gatekeeper and Hommel procedure. The first step is to evaluate the MACE non-inferiority of the albiglutide group vs the placebo group at a one-sided $\alpha=0.025$ level. If the result of non-inferiority is significant, MACE superiority, time-to-insulin and composite metabolic endpoint will be tested simultaneously using the Hommel procedure with $\alpha=0.05$. The above multiplicity control approach will preserve the study's nominal significance level of 0.05. The test order is illustrated in the diagram below.

Hommel Procedure for secondary endpoints is described below:

Three hypothesis tests for MACE superiority, time-to-insulin, and composite metabolic endpoint are subject to be adjusted by the Hommel procedure. Let $P(1)$, $P(2)$ and $P(3)$ represent the ordered p-values that $P(3) > P(2) > P(1)$ and $H(1)$, $H(2)$ and $H(3)$ are corresponding hypotheses.

If $P(3) < 0.05$, reject $H(3)$, $H(2)$, $H(1)$. End of test.

If $P(3) \geq 0.05$ and $P(2) < 0.05/2$, accept $H(3)$, reject $H(2)$, $H(1)$. End of test.

If $P(3) \geq 0.05$ and $P(2) \geq 0.05/2$ and $P(1) < 0.05/3$, accept $H(3)$, $H(2)$, reject $H(1)$. End of test.

If $P(3) \geq 0.05$, $P(1) \geq 0.05/3$ and $0.05/2 \leq P(2) < 0.05 \cdot 2/3$, accept $H(3)$, $H(2)$, reject $H(1)$. End of test.

If $P(3) \geq 0.05$, $P(2) \geq 0.05 \cdot 2/3$ and $P(1) \geq 0.05/3$, accept $H(3)$, $H(2)$ and $H(1)$.

Other Secondary Endpoints and Subgroup Analysis

The following secondary endpoints will provide supportive evidence for cardiovascular safety and will not use any multiplicity adjustment procedure.

- Components of primary endpoint (MACE = cardiovascular death, MI, stroke)
- MACE + urgent revascularisation for unstable angina
- Cardiovascular death or hospitalisation for heart failure

Other secondary endpoints which do not qualify for formal statistical hypothesis testing will be analyzed and have results presented with confidence interval and nominal p-values:

- Mean HbA1c at scheduled visits and change from baseline
- Mean body weight at scheduled visits and change from baseline
- Mean eGFR at scheduled visits and change from baseline
- Time to initiation of prandial insulin

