8.3.6.1. Primary Analysis

The primary analysis is an ITT analysis of the time to the first occurrence of MACE over the full duration of the study. Time to event analyses will be performed using Cox's Proportional Hazard regression with SAS PHREG with treatment group as the only covariate. Data for subjects without a primary event will be censored.

Treatment differences will be estimated via the hazard ratio and its 95% confidence interval (CI).

The hypothesis of non-inferiority of albiglutide relative to placebo group with hazard ratio less than 1.3 with respect to cardiovascular risk will be tested at the end of the study when ~611 first MACE events are cumulated.

The strength of evidence for non-inferiority will be determined by testing the hypothesis that the observed hazard ratio is significantly different from the null margin of 1.3 (one-sided $p < 0.025$ for such a test being equivalent to the upper 95% confidence limit after multiplicity adjustment for the hazard ratio being less than 1.3). The absolute risk difference per 100 PY and superiority p-value for albiglutide vs. placebo will also be presented.

The product-limit estimates of the probabilities (and their standard errors) of first MACE over time will be computed and displayed as Kaplan-Meier (KM) survival curves for albiglutide and placebo groups. The KM curves will also be presented corresponding to the above comparisons.

The total number of all MACE or any of its components will be analyzed by Poisson regression model. The incidence rate per 100 person-years, relative risk and their 95% CI will be presented. Number of subjects who experienced at least one event, 2 or 3 or more MACE or its components will also be summarized by treatment group.

As sensitivity analyses, the analyses described above will be repeated using events occur while on-treatment and events occur during the period of on-treatment plus 56 days post last dose.

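### Time to insulin, one of three alpha-controlled secondary endpoints, is tested without baseline HbA1c in the model; the test is valid but gives up power, by an amount the protocol's figures cannot fix

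*Protocol*

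**What the plan says.** Section 8.3.6.2 of the protocol says of subjects not on insulin at baseline that "time to insulin will be analyzed using a proportional Cox regression model similar to the primary MACE analysis". Section 8.3.6.1 defines the model being carried over: "Time to event analyses will be performed using Cox's Proportional Hazard regression with SAS PHREG with treatment group as the only covariate". Amendment 2 (Appendix 9, Section 11.9.2) adds the same rule to Section 8.3.3.2: "Time to event endpoints will be evaluated via the p-value from a Cox PH regression model with treatment as the only covariate". The Section 8 body text shown is from the version before Amendment 2, but that amendment's list of changes leaves the time-to-insulin item untouched.

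On status, Section 8.3.5 states: "Three hypothesis tests for MACE superiority, time-to-insulin, and composite metabolic endpoint are subject to be adjusted by the Hommel procedure". Section 8.3.1 adds: "Inference for the time to insulin endpoint will be made from the NI population".

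On the available baseline value, inclusion criterion 3 in Section 4.1 requires "HbA1c >7.0% (53 mmol/mol) based on the most recent documented laboratory assessment measured no more than 6 months prior to randomization". Section 3.2 lets an insulin regimen be started when HbA1c goals remain unmet after oral treatment has been adjusted.

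The only other provision for covariates in these time-to-event models, in Section 8.3.3, is exploratory and depends on imbalances seen in the data. The covariate set for the tested p-value is therefore fixed in the protocol and not left open to the analysis plan.

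**The concern.** The MACE model has been carried over to an endpoint of a different kind. Starting insulin is a treatment decision that the protocol itself ties to HbA1c. How far a subject is above goal at entry is therefore likely to predict when insulin starts, and that value is recorded before randomisation. If a prognostic covariate is left out of a Cox model, the estimated log hazard ratio moves toward zero while its standard error hardly changes, so the test loses power.

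What is at stake is the time-to-insulin claim and, through the Hommel rules, possibly the other two hypotheses. Suppose the other two p-values are 0.03 and 0.045 and time to insulin gives 0.04. All three are below 0.05, so all are rejected. Now reduce the time-to-insulin z-value by 8%: 2.05 × 0.92 = 1.89, p = 0.059. The largest p-value is now at least 0.05, the middle one (0.045) is at least 0.05 × 2/3 = 0.033, and the smallest (0.03) is at least 0.05/3 = 0.017. Under Section 8.3.5 nothing is rejected, MACE superiority included. This shows the mechanism and is not a forecast.

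**Working it through.** **The protocol's own figure.** The only power statement is for MACE non-inferiority (Section 8.2.1): margin 1.3, true hazard ratio 1.0, two-sided 0.05, 90% power, 1:1 allocation. Events = 4 × (1.960 + 1.2816)² / (log 1.3)² = 42.03 / 0.06883 = 610.6, that is 611. This reproduces, so the primary sizing is not in question. No power figure is given for time to insulin.

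**Assumptions needed, none of them in the protocol.**
- Non-insulin population: 40% of 9400 = 3760.
- Baseline HbA1c: above 7%, mean 8.7, SD 1.35.
- Follow-up: uniform over 1.7 to 3.7 years. The mean of 2.7 lies between the protocol's 2.2 and 3.2.
- Placebo subjects starting insulin: 10%, 25% or 40%.
- Hazard ratio per 1% HbA1c: 1.3, 1.6 or 2.0.
- Treatment hazard ratio given HbA1c: 0.80 or 0.70.

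**Attenuation.** Cox models with and without HbA1c were fitted to 6 × 400,000 simulated subjects per setting. Across all settings the unadjusted log hazard ratio was this share of the adjusted one:
- 96–99% at 1.3 per 1% HbA1c
- 88–96% at 1.6
- 78–86% at 2.0

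**Power.** With D events, power = Φ(|log HR| × √(D/4) − 1.960). Example: 25% placebo starts, 1.6 per 1%, adjusted HR 0.80, D = 863, √(863/4) = 14.69.
- Adjusted: 0.2231 × 14.69 = 3.278; 3.278 − 1.960 = 1.318; power 90.6%.
- Unadjusted: 0.2231 × 0.908 = 0.2026; 0.2026 × 14.69 = 2.976; 2.976 − 1.960 = 1.016; power 84.5%.

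All settings with adjusted HR 0.80 (unadjusted vs adjusted power, loss in points):

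| Placebo starts | 1.3 per 1% | 1.6 per 1% | 2.0 per 1% |
|---|---|---|---|
| 10% | 52.9 vs 54.0 (1.1) | 50.4 vs 54.2 (3.8) | 42.7 vs 54.3 (11.6) |
| 25% | 89.1 vs 90.6 (1.5) | 84.5 vs 90.6 (6.1) | 75.8 vs 90.9 (15.1) |
| 40% | 97.9 vs 98.6 (0.7) | 95.7 vs 98.6 (2.9) | 91.6 vs 98.7 (7.1) |

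With adjusted HR 0.70 the loss is 0 to 1.4 points when placebo starts are 25% or 40%. At 10% starts it is 0.7, 2.8 and 10.0 points.

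**Checks.** Direct simulation of 600 trials per setting at 25% starts and HR 0.80 gave 89.8 vs 91.8, 87.8 vs 91.7 and 74.3 vs 89.5. Each power has a Monte Carlo error of up to about 2 points. A separate simulation took 3800 subjects, a normal log-hazard covariate with SD 0.7 and 38% starting insulin. It gave mean log hazard ratios of −0.138 and −0.155 with a standard error of 0.053 in both models, and power of 73.5% vs 82.1%.

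**Type I error.** With no treatment effect, 25% starts and 1.6 per 1%, the unadjusted test rejected in 4.7% of 3000 trials at nominal 5%.

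**Hommel level.** These powers are for a single test at two-sided 0.05. At 0.05/3, the strictest level in Section 8.3.5, the losses with adjusted HR 0.80 run from 1.1 (35.9 vs 37.0) to 21.2 points (60.4 vs 81.6). Power under the full three-test procedure was not computed.

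**The case against.** The strongest reply is that nothing here is in error. An unadjusted Cox test in a 1:1 randomised trial is valid and common, and the relevant sections agree with one another. That stands. A reader might infer that the planned hazard ratio is biased or the test unsound. The documents do not support this: the unadjusted model estimates a marginal hazard ratio, the adjusted one a conditional hazard ratio, and type I error is kept. The complaint is lost efficiency only.

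A reader might also take HbA1c to be the main driver of insulin starts. The protocol does not say so. Section 3.2 makes insulin permissible when goals are unmet. Goals are individualised, the usual care provider decides, and other agents are available. The entry value may be a local result up to six months old. Each of these could weaken the association.

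The size is also open. Every input to it is assumed, and a negligible loss is as compatible with the protocol as a material one. No particular gain can be promised.

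Two further extensions fail. The metabolic composite is tested with a covariance-adjusted method, but no covariate is named, so it does not show that HbA1c adjustment is already the protocol's standard. Time to prandial insulin carries only a nominal p-value, uses a different population and was not calculated.

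None of this answers the narrower point: a likely prognostic value, already collected, is left out of an alpha-controlled test when including it costs almost nothing.

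**Conclusion.** The point holds as one of efficiency. The protocol fixes an unadjusted Cox model for time to insulin, and a prespecified adjustment for baseline HbA1c would be expected to raise power if HbA1c is prognostic.

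At two-sided 0.05 the loss is about 0 to 2 points when HbA1c is weakly prognostic (1.3 per 1%), or when the effect is large (adjusted HR 0.70) and at least 25% of placebo subjects start insulin. It rises to about 15 points when HbA1c is strongly prognostic (2.0 per 1%) and the effect is moderate (adjusted HR 0.80). Where the trial lies in that range cannot be determined from the protocol.

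Confidence is high on what the protocol specifies and on the direction of the effect, and low on its size. The Hommel knock-on to MACE superiority and the composite is possible under the stated rules, but its probability has not been estimated. If the analysis plan, which is not shown, already adjusts for HbA1c, the point is met.

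**What to change.** In Section 8.3.6.2, and in Section 8.3.3.2 as amended, state before unblinding that time to insulin in the non-insulin population is tested by a Cox model with treatment and baseline HbA1c as a continuous covariate. State also that this p-value enters the Hommel procedure and that the treatment-only model is a sensitivity analysis. Leave the MACE model unchanged. Section 8.3.6 already allows changes from the protocol's planned analysis to be recorded in the analysis plan.

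The cost is one sentence and one model term, with no new data. The one drawback is that the reported hazard ratio becomes conditional on baseline HbA1c, so the text should say so and show the marginal estimate beside it. Using the same model for time to prandial insulin is optional.

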2. OBJECTIVES AND ENDPOINTS

| Objectives | Endpoints |
|--|---|
| Primary | |
| To determine whether albiglutide is non-inferior with respect to MACE when added to glycaemic standard of care versus standard of care alone | 
 Time to first occurrence of MACE (cardiovascular death, myocardial infarction, or stroke) [Non-inferiority] |
| Secondary | |
| To supplement the primary objective by further characterization of the effects of albiglutide on cardiovascular outcomes | 
 Time to first occurrence of MACE [Superiority]^(1 see footnote) Time to first occurrence of the following: 
 MACE or urgent revascularisation for unstable angina The individual components of the primary endpoint Cardiovascular death or hospitalization due to heart failure |
| To evaluate the effects of albiglutide on metabolic management of type 2 diabetes | 
 Time to initiation of insulin of more than 3 months duration for those subjects not treated with insulin at study start ^(1 see footnote) Time to initiation of prandial insulin in those subjects on basal insulin at study start The proportion of subjects achieving glycaemic control (HbA1c ≤ 7.0% at final assessment) with no severe hypoglycaemic incidents and weight gain <5% of body weight ^(1 see footnote) The time to first occurrence of a clinically important microvascular event (see Section 6.2.4) Change in HbA1c Change in body weight Patient reported outcomes from TRIM-D/EQ5D |
| To evaluate the safety of albiglutide | 
 All cause mortality Non-fatal SAEs AEs leading to discontinuation of investigational product AE of special interest (see Section 6.2.3) Change in eGFR calculated using MDRD formula Change in blood pressure and heart rate |
| Exploratory | |
| To evaluate patient reported experience of diabetes treatment | 
 Patient reported outcomes from study specific questionnaire |

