6.2.4. Clinically Important Microvascular Events

Clinically important microvascular events are defined as the following: need for renal transplant or dialysis, new diabetes-related blindness, and procedures (laser photocoagulation or anti-vascular endothelial growth factor treatment or vitrectomy for diabetic retinopathy/eye disease). Clinically important microvascular events will be reported as recorded in the eCRF by the investigator without adjudication.

The AEs associated with the above outcomes or treatments should be reported separately as an AE or SAE according to the definitions in [Appendix 5](#).

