8.3.2. Analysis Data Set

For time to event data, censoring time for subjects who lost to follow-up is defined as following:

- For primary analysis, subjects who are lost to follow-up will be censored at the date of last evidence of confirmatory status for MACE events.
- For on-treatment analysis, censoring date will be the last dose date.
- For on-therapy analysis (on-treatment+56 days), censoring date will be the last dose date+56 days.
- For analysis of all cause of mortality, censoring date will be the latest date known alive.

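### Kaplan-Meier curves for starting insulin, starting prandial insulin and microvascular events treat deaths as censored, so the displayed probabilities are modestly too high

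*Protocol*

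**What the plan says.** - **Time to insulin** (Section 8.3.6.2, non-insulin population): "time to insulin will be analyzed using a proportional Cox regression model similar to the primary MACE analysis". The display is of "product-limit estimates of the probabilities (and their standard errors) of adding insulin over time", drawn as Kaplan-Meier curves by arm.
- **Microvascular composite** (same section): "Composite of microvascular events will be analyzed using a proportional Cox regression model / log-rank test and KM method similar to the primary endpoint". Time to prandial insulin among basal-insulin users is handled in the same way. The Amendment 2 change list removes the log-rank test from these two analyses, keeps the Kaplan-Meier method, and lists no change to the time-to-insulin item.
- **Censoring** (Section 8.3.6.1): "Data for subjects without a primary event will be censored". Section 8.3.2 adds a date rule, "For primary analysis, subjects who are lost to follow-up will be censored at the date of last evidence of confirmatory status for MACE events", and gives dates for the on-treatment, on-therapy and all-cause mortality analyses. It has no rule for death before insulin start or before a microvascular event.
- **Microvascular definition** (Section 6.2.4): "need for renal transplant or dialysis, new diabetes-related blindness, and procedures" for diabetic eye disease. Death is not a component.
- **MACE** (Section 8.3.6.1): "The product-limit estimates of the probabilities (and their standard errors) of first MACE over time" are also displayed. Section 2 makes cardiovascular death a component of MACE.

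No cumulative-incidence or competing-risk estimate appears in the protocol text at hand.

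**The concern.** A subject who has died can no longer start insulin or need eye treatment. Censoring that subject makes the product-limit estimator behave as if the event could still occur at the rate seen in survivors. One minus Kaplan-Meier then describes a hypothetical setting without death, whereas the protocol calls the quantity simply the probability of adding insulin.

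The curves are the only estimate over time, on a probability scale, that the protocol plans for these endpoints. Time to insulin is one of the three secondary endpoints in the Hommel family (Section 8.3.5), and delaying insulin is presented as a possible benefit (Section 3.4.2). Everyone enrolled has established cardiovascular disease, so some deaths will precede the event. If mortality differs between arms, so will the overstatement.

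**Working it through.** **Follow-up horizon, from the protocol's own figures.**
- Events: 4 × (1.960 + 1.2816)² / (ln 1.3)² = 610.6, so 611 as stated in Section 8.2.1 (90% power, one-sided 0.025, true hazard ratio 1.0, margin 1.3, 1:1 allocation).
- Mean follow-up: 611 / (9400 × 0.02) = 3.25 years and 611 / (9400 × 0.03) = 2.17 years, against 3.2 and 2.2 stated.
- The 2.0% row of Table 2 reproduces as 4.11, 4.36, 4.62 and 4.87 years with uniform accrual and a constant hazard, against 4.1, 4.4, 4.6 and 4.9 stated.

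The relevant times are therefore 2.2 and 3.2 years, with 4.9 years as the longest study duration in Table 2.

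**Formulas.** With a constant event hazard l and an independent constant competing-death hazard m:
- one minus Kaplan-Meier = 1 − exp(−l·t)
- cumulative incidence = l/(l+m) × [1 − exp(−(l+m)·t)]

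The first exceeds the second whenever m > 0. A simulation with l = 0.06, m = 0.02 and t = 3.2 gave a true incidence of 16.97% against a Kaplan-Meier target of 17.47%.

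**Insulin start, assumed 8% per year** (differences taken before rounding):

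| Years | Death per year | 1 − KM | Cumulative incidence | Excess (points) |
|---|---|---|---|---|
| 2.2 | 1.5% | 16.14% | 15.88% | 0.26 |
| 2.2 | 3% | 16.14% | 15.63% | 0.51 |
| 3.2 | 1.5% | 22.59% | 22.07% | 0.51 |
| 3.2 | 3% | 22.59% | 21.58% | 1.01 |

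Over a wider grid (start 3 to 10% per year, death 1 to 3% per year, 2.2 to 4.9 years) the excess runs from 0.07 to 2.5 points, or 1.1 to 7.3% relative. The upper end in points needs the highest rates and the longest duration together. The same formula applies to prandial insulin, for which the protocol also gives no rate.

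**Microvascular events, assumed 1% per year, death 1.5 to 3% per year.** At 2.2 years: 2.18% against 2.14 to 2.11%, or 1.7 to 3.3% relative. At 3.2 years: 3.15% against 3.08 to 3.00%, or 2.4 to 4.8% relative. In absolute terms this is at most 0.15 points.

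**MACE at the protocol's rates, assumed non-cardiovascular death 0.5 to 1.5% per year.** At 2.0% and 3.2 years: 6.20% against 6.15 to 6.05%. At 3.0% and 2.2 years: 6.39% against 6.35 to 6.28%. The largest excess is about 0.14 points, below one standard error: √(0.062 × 0.938 / 4700) = 0.35 points per arm.

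**Difference between arms, an illustration at 3.2 years.** Assume insulin start at 8% per year on placebo and 5% on albiglutide, with placebo deaths at 2% per year. The Kaplan-Meier difference is 7.80 points. The cumulative-incidence difference is 7.57 points with equal mortality, 7.48 with albiglutide deaths at 1.6% per year and 7.66 at 2.4%. The distortion is about 0.1 to 0.3 points.

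**The case against.** The strongest reply is that death-censoring is inferred for these endpoints. The censoring sentence sits in the primary-analysis section and concerns the primary event, the secondary endpoints only refer back to that analysis, and further detail is deferred to the reporting and analysis plan, which is not shown. That plan could add a competing-risk display. This stands as a caveat, but the protocol does not leave the estimator open: it names it, and for insulin it calls the result a probability. Under Section 8.3.6 a change would have to be recorded as a deviation.

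A second reply is that Kaplan-Meier display is a coherent companion to a Cox model, that inference rests on the Cox model, and that no landmark probability is specified. This is right, and it confines the point to the descriptive curves.

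Three stronger readings are tempting and are not supported:
- **That the MACE curve is materially too high.** Cardiovascular death is a MACE event, so only non-cardiovascular deaths are censored, and the excess is lost in sampling error. For MACE the protocol also plans an absolute risk difference per 100 person-years.
- **That the excess should be judged at 3 to 5 years.** Section 3.1 gives that range as the estimated maximum duration for an individual participant. Mean follow-up is 2.2 to 3.2 years, and at a MACE rate of 3.0% every study duration in Table 2 is 3.8 years or less. Section 4.2 also excludes subjects with a life expectancy under 5 years, which lowers mortality without removing it.
- **That the tests are compromised.** None of them uses these curves.

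**Conclusion.** The point holds as a minor one, for insulin, prandial insulin and microvascular events only. The direction is certain once deaths are censored. The size is modest: about 0.3 to 1.0 points for insulin across the mean follow-up range, and about 2 to 5% relative for microvascular events. These sizes rest on assumed event and death rates and on constant, independent hazards, because the protocol supplies no such rates. The conclusion also depends on reading the primary censoring rule into the secondary analyses. A reader might infer that the time-to-insulin result itself is biased, but the Cox hazard ratio and its place in the Hommel procedure stand as planned.

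**What to change.** In Section 8.3.6.2, replace the product-limit display for time to insulin, time to prandial insulin and the microvascular composite with Aalen-Johansen cumulative incidence by arm, with all-cause death as the competing event. State that deaths before the event are handled in this way in the display. The same display for MACE, with non-cardiovascular death competing, is optional. Keep the Cox models, the tests and the multiplicity procedure as they are.

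The cost is a wording change and a different curve estimator. All-cause mortality is already an endpoint and cause of death is already adjudicated, so no new data are needed. Sample size and alpha do not change.
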